#### **6.4 Accountability Procedures for the Study Product**

Cetuximab will be obtained and purchased as a commercial supply. The investigator or an approved representative (e.g. pharmacist) must maintain accurate records of dates and quantities of CTX dispensed under this study, and to whom study drug is dispensed.

Cetuximab should be stored in a secure area according to local regulations. Cetuximab must be dispensed only from official study sites by authorized personnel according to local regulations.

#### **Drug Destruction**

Opened vials must be disposed of at the site as chemotherapy or biohazardous waste, provided documented procedures for destruction are in place.

---

#### **6.5 Assessment of Subject Compliance with Study Product Administration**

Not applicable.

#### **6.6 Concomitant Medications/Treatments**

Prior to cetuximab (CTX) administration, participants will be premedicated with two medications, taking place 30-60 minutes prior to treatment:

- an H1 antagonist (50 mg of diphenhydramine) intravenously administered over 1 minute, taking place 30–60 minutes prior to the first dose; premedication will be administered for the subsequent cetuximab dose based upon clinical judgment and presence/severity of prior infusion reactions.
- Acetaminophen (650 mg orally) will be administered 30-60 minutes prior to chemotherapy as per University of Wisconsin Hospital and Clinics guidelines.

---

### **7 STUDY SCHEDULE**

See table in Appendix A. When calculating days of tests and measurements, the day a test or measurement is done is considered Day 0. Therefore, if a test were done on a Monday, the Monday one week later would be considered Day 7.

**COVID-19 testing:** Literature reports suggest that SARS-CoV-2 can be detected in the saliva of patients known to be infected with the virus. Therefore COVID-19 testing may be required per UWHC recommendations for aerosolizing procedures (research biopsy for correlative study).

## 7.1 Screening / Baseline Visit (Day -21 to 1)

### Study Visit 1 and 2

- Informed consent/HIPAA authorization obtained prior to any research procedures. Subjects will also be required to sign biobanking consent for banking of residual study samples. (research-related)
- Demographics (recorded for the study from medical records maintained as part of standard clinical care)
- Medical history including prior therapies and pathology (recorded for the study from medical records maintained as part of standard clinical care)
- Concomitant medications (recorded for the study from medical records maintained as part of standard clinical care)
- Physical exam, height (screening only), weight (recorded for the study from medical records maintained as part of standard clinical care)
- Vital signs (blood pressure, heart rate, temperature) (recorded for the study from medical records maintained as part of standard clinical care)
- ECOG performance status (recorded for the study from medical records maintained as part of standard clinical care)
- CBC with differential (recorded for the study from medical records maintained as part of standard clinical care)
- Blood chemistries (sodium, potassium, chloride, bicarbonate, BUN creatinine, glucose, AST, ALT, Alk Phos, T. bili, calcium, magnesium,
- T. protein and albumin (recorded for the study from medical records maintained as part of standard clinical care)
- Within 7 days prior to initiation of cetuximab: Urine pregnancy test for women of childbearing potential (WOCP). If the urine test is positive or cannot be confirmed as negative, a serum pregnancy test will be required. (standard clinical care for CTX administration)
- Adverse event evaluation (standard clinical care for CTX administration)
- Research biopsy for biological correlative studies
- Research blood draw for analysis of circulating tumor cells/biomarkers
- Measurement of tumor size via clinical assessment (research-related)

## 7.2 Intermediate Visits

### Study Visit 3, Cetuximab Dose 1

- Vital signs (blood pressure, heart rate, temperature) (recorded for the study from medical records maintained as part of standard clinical care for CTX administration)
- Weight (recorded for the study from medical records maintained as part of standard clinical care for CTX administration) Only required if screening/baseline visit > 7 days prior to treatment.
- CBC with differential (recorded for the study from medical records maintained as part of standard clinical care for CTX administration) Only required if screening labs > 7 days prior to treatment.
- Blood chemistries (sodium, potassium, chloride, bicarbonate, BUN creatinine, glucose, AST, ALT, Alk Phos, T. bili, calcium, magnesium, T. protein and albumin) (recorded for the study from medical records maintained as part of standard clinical care for CTX administration). Only required if screening labs > 7 days prior to treatment.
- Adverse event evaluation (standard clinical care for CTX administration)
- Administration of cetuximab (research-related)

### Study Visit 4, Cetuximab Dose 2 (7 days +/- 3 days from Study Visit 3)

- Vital signs (blood pressure only) (recorded for the study from medical records maintained as part of standard clinical care for CTX administration)
- Blood Chemistry: Potassium, calcium and magnesium (recorded for the study from medical records maintained as part of standard clinical care for CTX administration)
- Adverse event evaluation (standard clinical care for CTX administration)
- Administration of cetuximab (research-related)

### Study Visit 5, Safety Evaluation (within 7 days prior to surgery)

- Concomitant medications (recorded for the study from medical records maintained as part of standard clinical care for CTX administration)
- Physical exam (recorded for the study from medical records maintained as part of standard clinical care for CTX administration)
- Vital signs (blood pressure, heart rate, temperature) (recorded for the study from medical records maintained as part of standard clinical care for CTX administration)
- Weight (recorded for the study from medical records maintained as part of standard clinical care for CTX administration)

- ECOG performance status (recorded for the study from medical records maintained as part of standard clinical care for CTX administration)
- CBC with differential (recorded for the study from medical records maintained as part of standard clinical care for CTX administration)
- Blood chemistries (chloride, bicarbonate, BUN creatinine, glucose, AST, ALT, Alk Phos, T. bili, calcium, magnesium, T. protein and albumin) (recorded for the study from medical records maintained as part of standard clinical care for CTX administration)
- Adverse event evaluation (standard clinical care for CTX administration)
- Measurement of tumor size via clinical assessment (research-related)

### **SOC Surgery**

- Blood draw for pre-surgical measurement of circulating tumor cells/biomarkers in serum should be done within 1 day prior to surgery (Research procedure)
- During surgery, a portion of the resected tumor which pathology will not need for diagnosis (remnant tissue) will be obtained for study analysis

### **SOC Follow Up Visit 1, 1 month post-surgery (+/- 2 wk)**

- Blood draw for post-surgical measurement of circulating tumor cells/biomarkers in serum (Research procedure)
- Concomitant medications (recorded for the study from medical records maintained as part of standard clinical care)
- Physical exam (recorded for the study from medical records maintained as part of standard clinical care)
- Vital signs (blood pressure, heart rate, temperature) (recorded for the study from medical records maintained as part of standard clinical care)
- Weight (recorded for the study from medical records maintained as part of standard clinical care)
- ECOG performance status (recorded for the study from medical records maintained as part of standard clinical care)
- Serious adverse event evaluation (pertains to both research-related (section 9.1) AND standard clinical care)

### **SOC Follow Up Visit 2, 3 months post-definitive treatment\* (+/- 4 wk)**

- Physical exam (recorded for the study from medical records maintained as part of standard clinical care)

- Vital signs (blood pressure, heart rate, temperature) (recorded for the study from medical records maintained as part of standard clinical care)
- ECOG performance status (recorded for the study from medical records maintained as part of standard clinical care)
- Neck Imaging (findings recorded for the study from medical records maintained as part of standard clinical care)
- Blood draw for post-surgical measurement of circulating tumor cells/biomarkers in serum (research-related procedure)

### 7.3 Final Study Visit

#### **SOC Follow Up Visit 3, 12 months post-definitive treatment\* (+/- 4 wk)**

- Physical exam (recorded for the study from medical records maintained as part of standard clinical care)
- Vital signs (blood pressure, heart rate, temperature) (recorded for the study from medical records maintained as part of standard clinical care)
- Weight (recorded for the study from medical records maintained as part of standard clinical care)
- ECOG performance status (recorded for the study from medical records maintained as part of standard clinical care)
- Neck Imaging (findings recorded for the study from medical records maintained as part of standard clinical care)
- Blood draw for post-surgical measurement of circulating tumor cells/biomarkers in serum (research-related procedure)

\* Definitive therapy is defined as surgery alone, surgery + XRT or Surgery + chemoXRT

### 7.4 Withdrawal Visit

If a subject decides to withdraw from the study (and not just from protocol therapy) all efforts should be made to complete and report study assessments as thoroughly as possible. The treating investigator should contact the subject or a responsible relative by telephone to establish as completely as possible the reason for the study withdrawal. A complete final evaluation at the time of the subject's study withdrawal should be made with an explanation of why the subject is withdrawing from the study. If the reason for removal of a subject from the study is an adverse event, it will be recorded on the eCRF.

### 7.5 Unscheduled Visit

If a study subject should need an unscheduled visit, the treating physician should document the reason for the unscheduled visit (preferably in a clinic

note in the patient's chart). A complete description of the subject's symptoms and appropriate physical examination should be performed. In addition, the treating physician should document any recommendations and treatment plan for the subject at the time of the clinic visit. This information will be recorded on the eCRF.

## 8 STUDY PROCEDURES /EVALUATIONS

### 8.1 Study Procedures/Evaluations

#### **Criteria for Disease Assessment**

##### Assessment of Clinical Benefit Rate

Response assessment of cetuximab on clinical lesions will be determined by quantitative measurement performed by the treating physician pre-treatment and at the time of surgery. Response Evaluation Criteria in Solid Tumors (RECIST) 1.1 Committee criteria will be used to define clinical response prior to surgery.

##### Assessment of Disease Recurrence

Participants will be evaluated for evidence of recurrence on 2 occasions: 3 and 12 months post-definitive treatment (recorded for the study from medical records maintained as part of standard clinical care).

Given that all known disease will be surgically resected at the time of surgery, the only measure of relevance for this study will be recurrence of disease. Recurrence will be evaluated in this study using the new international criteria proposed by the RECIST 1.1 Committee. Note: Lesions are either measurable or non-measurable using the criteria provided below.

##### Measurable Disease

At baseline, tumor lesions/lymph nodes will be categorized measurable or non-measurable as follows (per RECIST 1.1).

##### **Tumor lesions:**

Measurable lesions are defined as those that can be accurately measured in at least one dimension (longest diameter in the plane of measurement is to be recorded) with a minimum size of:

- 10 mm by CT scan (CT scan slice thickness no greater than 5 mm)
- 10 mm measurement by clinical exam (lesions which cannot be accurately measured or are <10mm should be recorded as non-measurable)
- 20 mm by chest X-ray as >20 mm with conventional techniques (CT, MRI, x-ray) or as >10 mm with spiral CT scan. All tumor measurements

must be recorded in millimeters (or decimal fractions of centimeters). To be considered pathologically enlarged and measurable, a lymph node must be  $\geq 15$  mm in short axis when assessed by CT scan.

**Malignant lymph nodes:**

To be considered pathologically enlarged and measurable, a lymph node must be  $\geq 15$  mm in short axis when assessed by CT scan (CT scan slice thickness recommended to be no greater than 5 mm). At baseline and in follow-up, only the short axis will be measured and followed. The measurements will be recorded for the study from medical records maintained as part of standard clinical care.

**Non-measurable disease**

All other lesions (or sites of disease), including small lesions (longest diameter  $<10$  mm or pathological lymph nodes with  $\geq 10$  to  $<15$  mm short axis) as well as truly non-measurable lesions. Lesions considered truly non-measurable include: leptomeningeal disease, ascites, pleural/pericardial effusions, inflammatory breast disease, lymphangitic involvement of skin or lung, abdominal masses/abdominal organomegaly identified by physical exam that is not measurable by reproducible imaging techniques.

## **8.2 Laboratory Procedures/Evaluations**

### **8.2.1 *Clinical Laboratory Evaluations***

All clinical labs and evaluations done in this study are performed as standard medical care.

### **8.2.2 *Special Assays or Procedures***

**Research Biopsy**

Collection of specimen: In order to participate in this study, the tumor must be large enough to allow for the correlative study endpoints to be achieved. The minimum amount of tissue to achieve this is 2-3 core samples from the research biopsy with a strong preference for a cut-forceps biopsy (minimum recommended size: 2 x 2 x 2mm).

**Remnant Tumor Tissue**

Collection of surgical specimen: All specimens will go directly to the UWHC pathology department for diagnosis and processing. The biologic correlate study team will wait for the pathology team to access the specimen in the gross room and then will be given a portion of tissue that will not be required for diagnosis (i.e., remnant).

**Circulating Tumor Cells/Biomarkers**

**Collection of specimen:** We will collect blood for circulating tumor cell/or other biomarker identification at five timepoints: baseline, prior to surgical resection, one month post surgery, 3 and 12 months post definitive treatment. Approximately 10mL of blood will be collected in heparinized vacutainers (green top) at each time point.

### **Establishment of Patient-Derived Xenografts**

**Collection of specimen:** The research biopsy will also be used to establish patient-derived xenografts.

### **Determination of putative biomarkers of CTX sensitivity**

**Collection of specimen:** the research biopsy will also be used for correlative analysis of putative biomarkers of CTX sensitivity.

## **8.2.3 Specimen Preparation, Handling, and Storage**

### **Research Biopsy**

**Processing of specimen:** The tissue obtained for research biopsy will be placed in culture media or saline, stored at room temperature and provided to the biologic correlate study team within 3 hours post-surgery. The samples will be identified with the research study number and "research biopsy". The label will be stripped of all patient identifiers, such as MR number or dates. If squamous cell carcinoma is NOT confirmed, the tissue from the research biopsy will be relinquished to the TSB Biobank or surgical pathology based on clinical need.

Approximately 1/3 of the research biopsy will be formalin fixed and paraffin embedded. The remaining tissue will be used directly in mice to establish the first panel of PDX from patients with known sensitivity or resistance to cetuximab.

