### Schematic of Study Design:

The primary objective of this window of opportunity study is to test the hypothesis that low AXL expression correlates with clinical response to cetuximab in head and neck cancer patients. The secondary objective of this study is to further describe the safety of pre-operative administration of cetuximab. It is estimated that from the time of diagnosis/consult to resection of tumor is approximately 4-6 weeks. There is no absolute timeframe for study procedures to occur, although all protocol activities must be completed prior to resection.

This is a window of opportunity trial to study AXL and CTX in HNSCC patients. HNSCC patients who will undergo surgery will be identified. The tumor will be measured by the treating physician. A research biopsy will be taken and scored for Ki67 and proteins hypothesized to be involved in CTX resistance, such as AXL, EGFR and HER3. A section of the biopsy will be used for PDX development. A blood draw will be taken for circulating tumor cell analysis. Patients will receive two doses of cetuximab. Safety will be evaluated and blood will be collected for quantification of circulating tumor cells prior to resection. Remnant tissue from the resected tumor will be stained for Ki67 and compared to pre-treatment tumors. It will also be analyzed for proteins hypothesized to be involved in CTX resistance, such as AXL, EGFR and HER3. Patients will have blood draws for circulating tumor cells at 3 follow up timepoints: one month post-surgery, 3 months post definitive care and 12 months post definitive care. Patients will then continue on to standard of care.

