### **Tumor Tissue**

**Processing of specimen:** The study team will process and embed the fresh tissue obtained from the pathology department to an FFPE block for downstream studies. Alternatively, the biologic correlate study team will request 20 x 5 µm unstained FFPE slides from the diagnostic tissue after surgical pathology clinical review is complete. The specimens will be labeled with the research study number, "surgical resection," and section number, if applicable. The label will be stripped of all patient identifiers, such as the medical record number or dates.

Research Tissue samples and PDXs within the context of this protocol will be maintained under the supervision of [name] located at:  
University of Wisconsin  
[name]

[name]  
[name]

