### **Circulating Tumor Cells/Biomarkers**

Processing of specimen: The samples will be picked up by a member of the biologic correlative study team and transported to [name] lab. Upon arrival at the lab, PHI patient identifiers will be stripped from the sample and relabeled. The samples will be labeled with the subject's study ID number and coded time point (1- baseline, 2- pre-surgical resection, 3- one month post surgery, 4- three months post definitive-treatment, 5- twelve months post definitive treatment). Processing and storage of the circulating tumor cell samples within the context of this protocol will occur under the supervision of [name] lab located at:

Pharmaceutical Sciences Division  
University of Wisconsin School of Pharmacy  
[name]  
[name]  
[name]

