### **Determination of putative biomarkers of CTX sensitivity**

The biologic correlate study team will formalin fix and paraffin embed (FFPE) approximately one third of the research biopsy tissue to be used to assess putative biomarkers of CTX sensitivity (e.g. total and phosphorylated AXL, EGFR and HER3 expression using immunohistochemistry assays). The FFPE research and surgical specimens will be used to establish the change in Ki67 ( $\Delta$ Ki67).

Correlations between the change in Ki67 index ( $\Delta$ Ki67) and AXL expression and HER3 expression in the research biopsy will be performed. Further correlation between other biomarkers and AXL expression will be performed.

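### Tissue labels in Section 8.2.3 show patient number and time point, and nothing provides for re-coding or masked reading before Ki67 is scored

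*Combined protocol and SAP*

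**What the plan says.** Section 8.2.3 sets the labels specimen by specimen.

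- **Pre-treatment tissue (Research Biopsy):** "The samples will be identified with the research study number and 'research biopsy". The next sentence covers privacy: "The label will be stripped of all patient identifiers, such as MR number or dates".
- **Post-treatment tissue (Tumor Tissue):** "The specimens will be labeled with the research study number, 'surgical resection,' and section number, if applicable". Identifiers are removed here too. This tissue may reach the laboratory as unstained slides cut from the diagnostic block.
- **Blood (Circulating Tumor Cells/Biomarkers):** "The samples will be labeled with the subject's study ID number and coded time point". The protocol prints the meaning of the five codes.

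On handling, Section 8.2.3 (Determination of putative biomarkers of CTX sensitivity) says "The biologic correlate study team will formalin fix and paraffin embed (FFPE) approximately one third of the research biopsy tissue". On use, it says "The FFPE research and surgical specimens will be used to establish the change in Ki67". On reading, the Schematic of Study Design says only "A research biopsy will be taken and scored for Ki67 and proteins hypothesized to be involved in CTX resistance". Section 2 describes Ki67 as the percentage of cells that stain. Section 12.2 names image-analysis software for AXL; no such tool is named for Ki67.

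Section 4 describes a single-arm, open-label trial. No section mentions masked assessors, re-coding of slides or reading order.

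**The concern.** A Ki67 percentage depends on which fields and cells are counted. A reader who knows that a slide was taken after cetuximab may expect a lower value. A reader who also knows the patient's AXL score may expect a larger fall where AXL is low, because that is the trial's hypothesis. The first expectation would shift the mean change; the second would create a correlation with AXL. With one arm there are no untreated pairs in which such a drift would show.

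Ki67 is exploratory, but several results lean on it. Section 3.2.3 uses it as the measure of cetuximab response for the protein, RNA and circulating-tumor-cell markers. Sections 8.2.3 and 12.4 correlate the change in Ki67 with AXL, with HER3 and with the change in circulating tumor cells. An error in the Ki67 change would carry into each of these.

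**Working it through.** **What the labels reveal**

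1. *Time point.* The two tissue labels name the specimen type in words. One type exists only before cetuximab and the other only after it.
2. *Patient.* Section 8.2.3 does not define the research study number. Other identifiers are stripped, and each patient's two specimens must be matched to compute a change. So the number is presumably patient-specific. It is a pseudonym and does not itself display AXL or response, but it allows a link to both.
3. *Later masking.* The only relabelling step described is for blood, and it ends in a study ID plus a time code whose key is printed. No step between labelling and scoring removes the time point or patient from tissue.
4. *AXL in the primary comparison.* Section 3.2.1 uses pre-treatment AXL only. Every slide in that comparison comes from the research biopsy, so the time-point label cannot favour one patient over another.

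**How large a spurious correlation could be**

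The plan gives no figure for the variability of Ki67 or for reading error, so there is nothing of its own to reproduce. The one input from the documents is n = 36 (Section 12.2), taken to mean 36 complete pairs. The rest are assumptions: SD of the Ki67 change 15 percentage points, no true AXL effect, and a reading drift of b points per SD of AXL. The plan states no test level for these correlations; two-sided 5% is assumed.

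The spurious correlation is r = b / √(15² + b²).

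- b = 2: r = 2 / √(225 + 4) = 2 / 15.13 = 0.13
- b = 5: r = 5 / √(225 + 25) = 5 / 15.81 = 0.316

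The critical value, with 34 degrees of freedom and t = 2.032, is r = 2.032 / √(34 + 2.032²) = 2.032 / 6.175 = 0.329.

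The drift that would put r exactly at the critical value is b = 15 × 0.329 / √(1 − 0.329²) = 15 × 0.329 / 0.944 = 5.2 points per SD of AXL.

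The chance of a nominally significant result when the underlying spurious correlation is r, by Fisher's z with standard error 1/√33 (√33 = 5.745), is:

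- b = 5: atanh(0.316) × 5.745 = 1.88; 1.88 − 1.96 = −0.08; probability about 47%, against 5% with no drift
- b = 2: atanh(0.132) × 5.745 = 0.76; 0.76 − 1.96 = −1.20; probability about 12%

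**A uniform misreading**

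If every post-treatment slide were read 5 points low regardless of AXL, the mean change would shift by 5 points. Pearson's r would not move, because adding a constant leaves a correlation unchanged. The two biases therefore affect different outputs.

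**The case against.** The strongest reply is that the protocol is silent here, and silence is not a statement that reading is unmasked. Section 8.2.3 concerns preparation, handling and storage. It does not forbid re-coding, and no reader is named. A reader might infer that Ki67 and AXL are scored unmasked by the same team that is testing the AXL hypothesis. The documents do not support that: they say who embeds the tissue, not who scores it. What stands is that masking is not provided for, and that the labels as written would defeat it unless a step were added.

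Other limits also stand.

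- *AXL.* It would be wrong to conclude that the time-point label biases AXL in the primary comparison. Only pre-treatment AXL is used there, and software limits reader discretion without removing it. The remaining risk is that AXL is finalised when response is already known, which no label shows.
- *Circulating tumor cells.* The printed time code might suggest the same problem in the cell counts. The documents show no reader judgement in those counts, so the point is not extended to them. They enter only through their correlation with the Ki67 change.
- *Reach.* Section 2 mentions Ki67 alongside tumor size when describing response, but Section 3.2.1 bases the primary endpoint on clinical measurement. The primary and safety analyses and the sample size do not depend on Ki67.
- *Magnitude.* The SD and the drift are assumed, and even the larger example falls just short of the critical value.
- *Labels.* They serve traceability, since tissue may go back to surgical pathology or to the biobank.

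**Conclusion.** The point holds as a gap in protection for the exploratory Ki67 results. Section 8.2.3 prescribes labels that expose time point and, on the natural reading, patient, and no later step hides them from the person scoring Ki67. Bias could enter the mean change in Ki67 and its correlations with AXL, HER3 and change in circulating tumor cells. The time-point label does not touch the primary analysis.

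The size cannot be known from the documents. On the assumptions above (SD 15 points, 36 pairs, no true effect), drifts of 2 to 5 points per SD of AXL give a spurious r of about 0.13 to 0.32, with 0.329 as the critical value. This illustrates that a modest drift could matter; it does not estimate what will happen.

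The change should be made before scoring starts, because readings already taken cannot be masked afterwards.

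**What to change.** Keep the handling labels in Section 8.2.3 for traceability and add one paragraph on scoring, cross-referenced from the correlative analyses in Section 12.4:

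- Before scoring, re-code slides with random specimen codes. The study coordinator or the biostatistician holds the key.
- Read each patient's pre- and post-treatment Ki67 slides in one batch, in random order.
- Withhold patient, time point, AXL score and clinical response from the Ki67 reader until the scores are locked.
- Lock AXL scores before they are linked to response.

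The cost is a relabelling list and the added text, with no extra reader, tissue or procedure. There are two drawbacks. Scoring waits until both specimens of a pair are available. Masking of time point may also be incomplete, because a small biopsy and a resection specimen can look different. Patient, AXL and response can still be withheld, which guards against the AXL-dependent drift worked out above.
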